## Statistical Analysis Plan (SAP) - Phase 2 Segment

Table 2: Phase 2 Segment Schedule of Events

Tests and assessments	Sc	D0		Tel #1	Wk 4		Tel #2	Wk6	Tel #3	Wk 30	Wk 56	Illness	Illness	
	Screen a	Pre	Post	Day 0	Pre	Day 28 (±3d)	Post	Day 35 (±3d)	Day 42 (±5d)	Phone Call - Day 56 (±5d)	Day 210 (±5d)	Day 393 (± 5d)	COVID-19 assessment visit m	COVID-19 convalescent visit n
Informed Consent	X													
Inclusion/Exclusion Criteria	X													
Medical history	X	X												
Demographics	X													
Socio-behavioral Assessment	X													
Concomitant Medications	X	X		X	X		X	X	X	X	X	X	X	X
Physical Exam b	X	X			X			X		X	X	X	X	X
Vital Signs	X	X			X			X		X	X	X p	X p	X p
Height and Weight	X													
CBC with differential f	X	X			X			X				X		
Chemistry c	X	X			X			X				X		
HIV Serology		X												
Urinalysis Routine d	X	X			X			X				X		
Pregnancy Test e	X	X			X							X		
INO-4800 or Placebo + EP f		X			X									
Download EP Data g			X			X								
Adverse Events h	X	X	X	X	X	X	X	X	X	X	X	X	X	X
Cellular Samples i		X						X		X	X			X
Humoral Samples j		X						X		X	X			X
SARS-CoV-2 Serology k	X													
SARS-CoV-2 RT-PCR (Saliva and Swab)	X l											X l	X l	
Distribute Diary			X			X								
Review/Collect Diary o				X	X		X	X						

## Statistical Analysis Plan (SAP) - Phase 2 Segment

- a. Screening assessment occurs from -30 days to -1 day of Day 0.
- b. Full physical examination only at Screening and Day 393 (or EOS). Targeted physical exam at other indicated visits.
- c. Hemoglobin A1c collected at screening only. Chemistry includes Na, K, Cl, HCO3, Ca, PO4, glucose, BUN, Cr, alkaline phosphatase, AST, ALT, LDH, total bilirubin.
- d. Dipstick for glucose, protein, and hematuria. Microscopic examination should be performed if dipstick is abnormal.
- e. Serum pregnancy test at Screening. Urine pregnancy test at other visits.
- f. Intradermal injection(s) in skin preferably over deltoid muscle, or alternately over anterolateral quadriceps muscle, followed by EP at Day 0 and Day 28.
- g. Following administration of INO-4800 or placebo, EP data will be downloaded from the CELLECTRA® 2000 device and provided to Inovio.
- h. AEs to be collected from time of consent to Day 56; SAEs, MAAEs, and AESIs to be collected from time of consent to EOS.
- i. On Day 0, cellular sampling requires 64 mL of whole blood (8 Cell Preparation Tubes (CPT), each 8 mL of whole blood) prior to 1st dose. At all other time points, collect 32 mL of whole blood (4 CPT tubes, each 8 mL of whole blood).
- j. On Day 0, humoral sampling requires a total of 17 mL of whole blood (two 10-mL red top serum collection tubes, each 8.5 mL of whole blood, to produce eight serum aliquots of 1 mL each). At all other time points, collect 8.5 mL of whole blood in a single 10-mL red top serum collection tube to produce four serum aliquots of 1 mL each.
- k. SARS-CoV-2 antibody.
- l. Saliva specimen at Screening; Nasal swab and saliva specimens at COVID-19 assessment and convalescent visits. Genotyping may also be performed on sample(s) collected at the COVID-19 assessment visit.
- m. Subjects will be evaluated during a "COVID-19 assessment visit" when acute COVID-19 is suspected. The assessment visit may be performed in the clinic, in the subject's vehicle or at the subject's home and should be completed within 3 days of symptom onset or within 3 days of a positive result of a SARS-CoV-2 test.
- n. For subjects with confirmed SARS-CoV-2 infection during the trial, a convalescent visit should be scheduled approximately 28 days after symptom onset, or in the absence of symptoms, the date of positive SARS-CoV-2 test. If acute symptoms are ongoing, the site should follow up with the subject via phone call or an unscheduled visit after symptom resolution or stabilization.
- o. Diary should be reviewed at the 7-day post-dose phone call and collected at the next in-office visit.
- p. Vital signs to be performed at COVID-19 assessment and convalescent visits include temperature, respiration rate, heart rate and oxygen saturation.

### **3 Study Endpoints**

#### **3.1 Primary endpoints**

- Antigen-specific cellular immune response measured by IFN-gamma ELISpot
- Neutralizing antibody response measured by a pseudovirus-based neutralization assay

#### **3.2 Secondary endpoints**

- Incidence of solicited and unsolicited injection site reactions
- Incidence of solicited and unsolicited systemic adverse events (AEs) by system organ class (SOC), preferred term (PT), severity and relationship to investigational product
- Incidence of serious adverse events (SAEs)
- Incidence of adverse events of special interest (AESIs)

#### **3.3 Exploratory endpoints**

- Antigen-specific cellular immune response measured by flow cytometry.
- Expanded immunological profile which may include additional assessments of T and B cell numbers and molecular changes by measuring immunologic proteins and mRNA levels of genes of interest as determined by sample availability

### **4 Sample Size and Power**

The phase 2 segment of this trial was not powered to conduct any formal hypothesis testing.

### **5 Analysis Populations**

#### **5.1 Analysis Population**

##### **5.1.1 Intention-To-Treat population (ITT)**

The ITT population includes all subjects who are randomized. Subjects in this sample will be grouped to treatment arms as randomized.

##### **5.1.2 Modified Intention-To-Treat population (mITT)**

The mITT population includes all subjects who receive at least one dose of Study Treatment. Subjects in this population will be grouped to treatment arms as randomized.

##### **5.1.3 Safety population (Safety)**

The safety analysis population includes all subjects who receive at least one dose of Study Treatment. Subjects will be analyzed according to the treatment received. If a subject receives one dose of one

## Statistical Analysis Plan (SAP) - Phase 2 Segment

treatment and one dose of another treatment accidentally, the subject will be analyzed according to the treatments received.

### 5.1.4 Per-Protocol population (PP)

The per-protocol (PP) population includes all subjects who receive all doses of Study Treatments and have no protocol violations. Subjects in the PP population will be grouped to treatment arms as randomized.

Subjects excluded from the PP population will be identified and documented prior to unblinding of the trial database. Analyses on the PP population will be primary for the analysis of immunogenicity in the Phase 2 segment of this trial.

### 5.2 Protocol deviations/violations and exclusions from analysis sets

Protocol deviation data will be captured in the clinical trial management system. Extracts of all protocol deviations will be reviewed periodically and prior to final analysis. All protocol deviations and the exclusion of participants from analysis sets will be identified prior to unblinding, through clinical review input provided by the sponsor, using the following sources of information:

- Supportive participant listings, provided by the ICON statistician based upon data recorded in the clinical trial management system

Further, deviations from the protocol will be classified as major or minor. Classification of major and minor protocol deviations is determined prior to participant enrollment and is outlined in detail in the protocol deviation criteria documentation managed by the clinical trial management team.

## 6 Statistical Considerations and Analysis

### 6.1 Derived Variables

The below table provides the list of derived variables for demographic and baseline characteristics, various duration derivations, baseline derivation and other important derivations applicable for this segment of the trial.

**Table 3: Derived Variables**

Demographic and Baseline Characteristics	
Body Mass Index	Weight (kg) / [height (m)] ^2
Age	Calculated at the time of informed consent. Sample SAS code to calculate age is: age = floor ((intck('month', date of birth, informed consent date) – (day(informed consent date) < day(date of birth)) ) / 12)

Baseline	Baseline is defined as the last measurement prior to the first treatment administration
Derivation of Durations	
Study day at any visit	Date of interest – date of first dose. One day is added if the difference is $\geq 0$ .
Duration of any events	End Date of Event – Start date of event + 1
Other Derivations	
Incidence in a group	The proportion of the participants experiencing the outcome of interest compared to the total number of participants at risk of experiencing the outcome of interest. (e.g. the incident rate of SAEs after vaccination are the number of participants with an SAE reported after vaccination divided by the number of participants that received the vaccination).
Geometric Mean Fold Rise (GMFR)	The ratio of the geometric mean post-baseline result to the geometric mean baseline result of a particular lab/assay result.

### 6.2 Handling of missing data and outliers

#### 6.2.1 Missing data analysis methods

No imputations will be conducted for missing data.

##### 6.2.1.1 Handling of missing or incomplete dates

###### Imputation rules for missing or partial adverse event start/stop dates

- If the AE start date day is missing (month and year provided) then set the date to the first of the month, unless the month and year are the same as the first dose. In this case, set the date to the date of first dose.
- If the AE start month is missing (day and year provided) then set the month to January, unless the day and year are the same as the year of the first dose. In this case, set the date to the date of first dose.
- If the AE start date day and month are missing (year is provided) then set the month and day to January 1, unless the year is the same as the year of the first dose. In this case, set the date to the date of first dose.
- If the AE end date day is missing (month and year provided) then set the date to the last day of the month.

- If the AE end date month is missing (day and year provided) then set the date to the latest calendar month consistent with the day.
- If the AE end date day and month is missing (year is provided) then set the date to December 31.
- If the year of the AE start date or AE end date are missing, then a query to the site must be made to gather additional information.
  - If the start date is completely missing, then set the start date to the date of first dose. If the end date is completely missing, then set the end date to the date of latest follow-up.
  - If the start date day is missing (month provided), then set the date to the first of the month, unless the month is the same as the first dose. In this case, set the date to the date of first dose. If the end date day is missing (month provided), then set the date to the last day of the month.
  - If the start date month is missing (day provided), then set the month date to January, unless the day is the same as the first dose. In this case, set the date to the date of first dose. If the end date month is missing (day provided), then set the date to the latest calendar month consistent with the day.
  - If the start date year is missing (day and month provided), then set the year to the year in which the patient was first screened, unless the day and month are the same as the first dose. In this case, set the date to the date of first dose. If the end date year is missing (day and month provided), then set the date to the latest calendar year in which the patient is followed.

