## Statistical Analysis Plan (SAP) - Phase 2 Segment

---

AEs will be classified as pre-treatment or treatment emergent (TEAE) defined as follows:

- Pre-treatment: any AE that started before the first dose date of the study treatment
- TEAE: any AE that was newly developed at or after the first dose date of study treatment

Details for imputing missing or partial start dates of adverse events are described in [section 6.2](#).

AE summary tables will include the following:

- All TEAEs
- Related TEAEs (AE will be defined as related if causality is either probable, possible, or definite)
- TEAEs by maximum severity
- TEAEs leading to treatment discontinuation
- Serious TEAEs
- TEAEs leading to death

All AEs including injection-site reactions will be summarized among the Safety Population by frequency per treatment arm. These frequencies will be presented overall and separately by dose, and will depict overall, by system organ class and by preferred term, the percentage of subjects affected.

Where a subject has the same adverse event, based on preferred terminology, reported multiple times in the treatment period, the subject will only be counted once at the preferred terminology level in adverse event frequency tables.

Where a subject has multiple adverse events within the same system organ class in the treatment period, the subject will only be counted once at the system organ class level in adverse event frequency tables.

Adverse events by severity and separately by relationship will be summarized based on the most intense event during the treatment period and strongest relationship to study treatment, respectively.

The main summary of safety data will be based on events occurring within 30 days of any dose. For this summary, the frequency of preferred term events will be compared between study arms with risk differences and 95% confidence intervals, using the method of Miettinen and Nurminen. As this analysis will use many event categories, and produce many confidence intervals, caution should be exercised when interpreting these confidence intervals. Separate summaries will be based on events occurring within 7 days of any dose and regardless of when they occurred.

The following sample of SAS code will be used to construct confidence intervals of the risk difference with the method of Miettinen and Nurminen:

```
proc freq data = <DATASET>;
  tables armcd * <OUTCOME> / riskdiff(CL= MN);
```

---

```
weight <COUNT>;  
run;
```

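### AE start-date imputation in both SAPs has no floor at first dose, so some post-dose events with a missing year, or on one reading a missing month, are dated before dosing and lose TEAE status

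*SAP*

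**What the plan says.** Section 6.2.1.1 of the Phase 2 SAP and section 3.5.2.1 of the Phase 3 SAP give the same AE start-date rules:

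- **Month missing, day and year known:** "set the month to January, unless the day and year are the same as the year of the first dose". The exception gives the first-dose date.
- **Day and month missing, year known:** "set the month and day to January 1, unless the year is the same as the year of the first dose". Again the exception gives the first-dose date.
- **Year missing:** "then a query to the site must be made to gather additional information". The fallback, with day and month known, is "set the year to the year in which the patient was first screened, unless the day and month are the same" as those of first dose, in which case the first-dose date is used.
- **Year and month missing, day known:** "then set the month date to January, unless the day is the same as the first dose". No year is named.

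Phase 2 section 7.7.1 then classifies by start date: "Pre-treatment: any AE that started before the first dose date of the study treatment". An event beginning at or after first dose is treatment-emergent. Phase 3 section 5.4.1 defines both classes in the same way. Both sections refer to the imputation rules for partial start dates.

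**The concern.** The usual aim of such rules is that an event which could have begun after dosing counts as treatment-emergent unless there is evidence that it did not. Here the only protection is that the known date parts coincide with those of first dose. Coincidence is not a floor: an event with any other day, or any other day and month, can be dated before dosing even though its known parts allow a later onset.

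Two features stand out. The missing-year fallback uses the screening year, although participation always runs into a later calendar year. And on the literal reading of the missing-month rule, a record with more information is treated less cautiously than one with less, because a year match is enough only when the day is missing as well.

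At stake is the TEAE count, and probably the 30-day main safety summary and the 7-day summary, which also depend on the start date. After Day 56 only SAEs, MAAEs and AESIs are collected, so a late event hit by the missing-year rule would be one of these.

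**Working it through.** The SAPs state no figure on this point. The check applies the rules as written to example dates and then to a full calendar. All calendar dates are assumptions, since no dosing calendar is given.

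**Inputs.** Screening is 1 to 30 days before Day 0 (Phase 2 Table 2, note a; Phase 3 Appendix A, note a, which also allows a combined visit). Follow-up runs to Day 393 (Phase 2 section 2.7; Phase 3 section 1.2.4). All AEs are collected from consent to Day 56; SAEs, MAAEs and AESIs to end of study.

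**Missing year**

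1. Screened 20 Dec 2020, dosed 5 Jan 2021, recorded as 10 Feb with year unknown. Day and month differ from 5 Jan, so the year becomes 2020. The imputed start is 10 Feb 2020, ten months before consent, and the event is pre-treatment.
2. Screened 1 Dec 2020, dosed 15 Dec 2020, true onset 5 Jan 2021. Imputed start: 5 Jan 2020, pre-treatment. Day 56 is 9 Feb 2021. Of the 57 onset days from Day 0 to Day 56, the 40 from 1 Jan to 9 Feb all go to 2020: 40/57 = 70.2%.
3. Screened 24 Feb 2021, dosed 10 Mar 2021. Every Day 0-56 onset is in 2021, so none is misplaced. Over Day 0-393 (394 days), onsets from 1 Jan to 9 Mar 2022 go to before dosing: 31 + 28 + 9 = 68, and 68/394 = 17.3%.

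**Missing month**

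4. Dosed 15 Mar 2021, recorded as `20-unknown-2021`. On the literal reading (day and year must both match), the start becomes 20 Jan 2021. That is 54 days before dosing, although screening could not begin before 13 Feb. The less complete record `unknown-unknown-2021` becomes 15 Mar 2021 and is a TEAE. On a year-match reading, both become 15 Mar 2021.
5. Dosed 10 Mar 2021, literal reading, Day 0-56. Only 10 Mar and 10 Apr match on day, so (57 - 2)/57 = 96.5% are dated before dosing. On the year-match reading, none is.

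**Enumeration.** Take every first-dose date in 2021 and every true onset day: 365 x 57 = 20,805 pairs for Day 0-56 and 365 x 394 = 143,810 for Day 0-393. The table gives the share of true post-dose onsets imputed before first dose, among records with the stated pattern.

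| Missing part | Day 0-56 | Day 0-393 |
|---|---|---|
| Month, literal reading | 85.0% | 41.1% |
| Month, year-match reading | 0% | 0% |
| Year, screening 1 day before dosing | 7.9% | 46.7% |
| Year, screening 30 days before dosing | 15.7% | 54.4% |
| Day only | 0% | 0% |
| Day and month, year known | 0% | 0% |

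The last two rows show that the plan already protects post-dose events for the commoner patterns. The gap lies in the other rules. The rule for year and month both missing could not be enumerated because it names no year; it too has no floor.

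**The case against.** The strongest reply is that the missing-month exception is a drafting slip. A day cannot equal a year, and the next rule works on a year match alone. If that was meant, the year-known missing-month rule misplaces nothing. This stands as far as it goes. The literal reading remains possible, however, since the rule with the year also missing matches on day, and two programmers could code the sentence differently. The missing-year rule fails on either reading.

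Second, a missing year triggers a site query first. That is a real safeguard and makes the fallback rare, but the fallback is what the plan prescribes when the query fails.

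Third, a known day with an unknown month, or a known day and month with an unknown year, is unusual, and Phase 2 diaries are reviewed 7 days after each dose. I accept this; it limits the size and not the existence of the error.

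A reader might infer three stronger things that the documents do not support:

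- **That every such record is misdated.** The table shows shares well short of 100%.
- **That the events vanish from all safety output.** All subject data are listed. Both SAPs also say that all AEs will be summarised, and plan a summary regardless of timing, so the events may appear there.
- **That the rules can only undercount.** On the literal reading, an onset on 10 Feb 2021 with the month missing and first dose on 10 Mar 2021 matches on day and year. It becomes 10 Mar and is counted as a TEAE. The rules for a missing day, for day and month missing, and for a wholly missing date can also move pre-dose events to first dose.

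**Conclusion.** The point holds as a minor defect in both SAPs. Some post-dose AEs with a missing year and, on the literal reading, a missing month are imputed before first dose, sometimes before consent. They then drop out of the TEAE tables and probably the post-dose windows. The missing-year part does not depend on how the garbled sentence is read; the missing-month part does.

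The percentages assume first-dose dates and onsets spread evenly over the stated ranges. They are conditional on the missing pattern and are not expected losses of events. The documents give no frequency, and few records are likely to be affected. The rules are the same in every arm, so the plan gives no ground for inferring a distorted comparison between arms; the main effect is a TEAE count that is somewhat too low.

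**What to change.** Replace the start-date rules in Phase 2 section 6.2.1.1 and Phase 3 section 3.5.2.1 with one principle: if the known date parts allow onset on or after first dose, impute the earliest such date, unless the known parts, the AE end date, or the visit at which the AE was recorded (Screening or Day 0 pre-dose) show that it began before first dose. If the only candidate on or after first dose falls after the end date or the recording visit, the event began before dosing and comes under the same exception.

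The recording visit is needed because AEs are collected before dosing. Without it, an ongoing event noted pre-dose on 15 Mar 2021 as `20-unknown-2021` would be moved to 20 Mar and counted as a TEAE.

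Reword the missing-month exception to match, and state which year applies when month and year are both missing. Under the new rule, no true post-dose onset with correctly recorded parts is dated before first dose, by construction. The worked records become 20 Mar 2021 (case 4), 10 Feb 2021 (case 1) and 5 Jan 2021 (case 2). The cost is a few sentences in each SAP and a small macro change; no new data are needed.

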### Imputation rules for missing or partial prior/concomitant medication start/stop dates

- Start dates will not be imputed.
- Partial stop dates of prior/concomitant medications will be assumed to be the latest possible date consistent with the partial date. If day, month, and year are missing assign 'continuing' status to the stop date.

## 7 Statistical Methods

### 7.1 General statistical conventions

All statistical procedures will be completed using SAS version 9.4 or higher.

Unless otherwise stated, all statistical testing will be two-sided and will be performed using a significance (alpha) of 0.05. Two-sided 95% confidence intervals (CI) will be provided when relevant.

Continuous variables will be summarized using descriptive statistics, including number of subjects (n), mean, median, standard deviation (SD), minimum, and maximum. Means and medians will be rounded to one more

decimal place than what is reported in the data. Standard deviations will be rounded to two more decimal places than what is reported in the data.

For categorical variables, summaries will include counts of subjects and percentages. Percentages will be rounded to one decimal place.

For summary purposes, baseline is defined as the last measurement prior to the first treatment administration. All summaries will be presented by treatment group, unless otherwise specified.

All subject data, including those derived, will be presented in individual subject data listings. Unless otherwise stated, unscheduled visit results will be included in date/time chronological order, within patient listings. All listings will be sorted by investigational site, subject ID, date/time and visit. The treatment group as well as the patient's sex and age will be stated on each listing. Unless otherwise stated, data listings will be based on all subjects randomized (ITT Population).

